1.0 INTRODUCTION

1.1 OVERVIEW

Hematopoietic cell transplantation (HCT), commonly known as bone marrow transplantation, is the only potentially curative treatment for many advanced hematologic malignancies.¹⁻³ It is a

Version 8 , 11/16/2020

highly technical inpatient procedure that is only available at select centers in the United States: those that have the capacity for collecting and storing hematopoietic stem cells, as well as caring for patients before the new immune cells take hold. For this reason, many patients who undergo HCT live at great distances from their HCT center. Moreover, after hospital discharge, the first 180 days post-HCT are critical. Patients must be watched closely for infections and/or the development of graft-versus-host disease (GVHD) and specialized anti-rejection medications must be tightly managed. For those who live far away, the need for close follow-up for such a long period can cause a great burden in terms of familial finances, impact on caregivers, and compromised quality of life.^{4,6}

One way of potentially ameliorating these effects is to allow some of the post-HCT care to be provided by non-HCT oncologists who practice closer to where patients live. Such a model could reduce patient-centered burdens post-HCT; however, it is not known if, given its complexity, post-HCT care can truly be “shared” between HCT specialists and local oncologists without compromising HCT-related outcomes. We aim to assess the effectiveness of a Shared Care program which allows patients to receive half of their post-HCT care at the HCT center, and the other half with their local oncologist.

1.2 BACKGROUND AND RATIONALE

HCT has become a standard treatment option for many advanced blood cancers. According to the Center for International Blood and Marrow Transplantation Research (CIBMTR), the overall number of allogeneic HCTs in adults in the US surpassed 8,000 per year in 2013, with 8,351 in 2015.⁷ In addition, likely due to advances in approaches to infectious disease and other HCT complications, outcomes have significantly improved. Such good news about the increasing availability of HCT has contributed to improvement in the length of life of those transplanted.⁸

Although many HCT survivors eventually return to baseline health, those who undergo an allogeneic procedure (receiving cells from another person) are at particular risk of experiencing short- and long-term effects of the procedure itself. These include rare and common infections, GVHD (acute or chronic), and many other issues that, in addition to the ever-present concern for disease relapse, require diligent monitoring by the HCT team after discharge from the initial inpatient procedure. Usual care for patients after HCT at most centers consists of returning to the HCT center weekly for the first three months and bi-weekly for the next three months (except for emergency care). This intense visit schedule for the first 180 days can be very difficult for patients who live far away in terms of their quality of life (QOL) and personal financial well-being, and distance from transplant center may even impact survival. For example, it has been shown that long driving time (≥ 160 min) to the HCT center is associated with a decreased likelihood of being disease-free one year after the procedure.⁸

Until recently it was not known if living far away from the HCT center was associated with compromised post-HCT familial finances and/or QOL. A pilot study assessing patient and caregiver costs in the first three months after HCT (n=30)⁹ revealed that the median out-of-

Version 8 , 11/16/2020

pocket cost was over \$2,000 (range: \$199 to \$13,769), and that patients/caregivers who required temporary lodging had higher expenses compared with those who did not. Another study of allogeneic HCT survivors (assessed a median of 2.3 years after the procedure) found that 47% reported ongoing financial burden after HCT – defined as household income decreased by >50%, selling/mortgaging home, or withdrawing money from retirement accounts.¹⁰ With 268 respondents (56% response rate), 73% reported that having had an HCT “hurt them financially.” These analyses show **familial financial hardship to be prevalent shortly after HCT, but do not reveal if it is associated with worse patient-reported outcomes such as QOL during this period.**

We recently completed a multi-site survey of adult patients approximately 180 days after HCT (DFCI protocol 14-144; n=325; 72% response rate) to assess the familial financial hardship they might experience after HCT, its sources, and its effect on patient QOL. Income decline was reported by 46% of patients from DFCI center as well as two others (Mayo Clinic in Phoenix, AZ and Roswell Park in Buffalo, NY); 57% reported financial hardship after HCT (defined as dissatisfaction with present finances, difficulty meeting monthly bill payments, or not having enough money at the end of the month), and 16% reported extreme hardship (all three).^{4,11,12} In multivariable models controlling for income, **those reporting HCT-related costs such as travel to the HCT center were more likely to report post-HCT income decline and extreme financial hardship.** Moreover, reporting financial hardship was in turn associated with reporting QOL below the median (OR 3.0 [1.8, 5.0]), health status below the median (OR 2.2 [1.4, 3.6]), and stress above the median (OR 2.1 [1.3, 3.5]) as assessed by the PSS-4, a validated measure of perceived stress.¹³⁻¹⁵

At most HCT centers, patients are required to return to the center itself for the bulk of their follow-up even if it is very far away from their home. Another care delivery model used by some centers is to discharge patients completely to local providers (primary care or oncology) shortly after the procedure. Unfortunately, primary care physicians and local non-HCT oncologists often lack sufficient education to manage complex HCT issues, and such models can also leave patients feeling unsupported after having been in the hospital for almost a month after their initial procedure.^{16,17} In contrast, we have created a new post-HCT delivery model in which both local oncologists and transplant oncologists work together to care for patients after HCT. We call this model “Shared Care,” and plan a randomized controlled trial to test its effectiveness in improving patient-reported outcomes (PROs).

2.0 OBJECTIVES

This study will assess the effectiveness of a shared approach to post-HCT care to Usual Care (all care at DFCI) with respect to highly-relevant PROs and traditional HCT outcomes. We aim to:

1. Compare highly-relevant PROs for Shared versus Usual Care at 180 days post-HCT.
2. Compare 100-day non-relapse mortality (NRM) for patients in Shared Care versus Usual Care.

3.0 RESEARCH SUBJECT SELECTION

Overall, 324 patients will be recruited and consented on-site at DFCI to participate in this randomized controlled trial. Annually, approximately twenty participants will be recruited to share care with each site. Post-HCT visits for the 162 patients randomized to Shared Care will occur about 50% at Dana-Farber and 50% at the local site, supported through an innovative web-based provider communication portal (ACT.md). The local sites are:

1. Lifespan Cancer Institute (Providence, RI; 21 participants per year)
PI: [name] ([contact])
IRB Manager: [[name]](mailto:[contact]) ([contact])
2. Dartmouth-Hitchcock (Lebanon, NH; 20 participants per year)
PI: [name] ([contact])
IRB Manager: [name] ([contact])
3. New York Oncology Hematology (Albany, NY; 20 participants per year)
PI: [name] ([contact])
IRB Manager: [name] ([contact])
4. New England Cancer Specialists (Brunswick, Maine; 14 participants per year)
PI: [name] ([contact])
Covered by Dana-Farber IRB
5. Eastern Maine Medical Center (Brewer, Maine, 14 participants per year)
PI: [name] ([contact])
IRB Manager: [name] ([contact])
6. DFCI Community Cancer Care and Satellites (Weymouth and Milford, MA; 20 participants per year)
PI: [name] ([contact])
Covered by Dana-Farber IRB

Inclusion criteria include:

1. Age \geq 18 years of age
2. Scheduled to receive an allogeneic HCT at the Dana-Farber Inpatient Hospital or BWH under the care of a DFCI physician.
3. Residence in New York, Maine, New Hampshire, Vermont, Connecticut, Rhode Island, or Massachusetts.
4. Referred from one of the above six centers, or chooses to receive care at one of the six centers.
5. Ability to read English (to fill out standard QOL forms)

Exclusion criteria include:

1. Age $<$ 18 years of age
2. Scheduled to receive an autologous HCT

Version 8 , 11/16/2020

3. Has received an allogeneic transplant in the past; scheduled to receive a second allogeneic transplant
4. Did not receive an allogeneic HCT at Dana-Farber
5. Does not live in New York, Maine, New Hampshire, Vermont, Connecticut, Rhode Island, or Massachusetts.

4.0 RESEARCH SUBJECT ENTRY

Potential study participants will be informed of the study during their first consultation with an HCT physician and/or nurse at DFCI (an information sheet [Appendix A] will be added to the *Guide to Transplant* binder). Study consent will take place at the same time patients consent to HCT, which is always on a subsequent visit. Potential participants will be given the opportunity to ask questions, opt out of consideration, and take a consent form home to discuss further with their family and/or other clinicians. We will also be clear that enrollment does not guarantee assignment to **Shared Care**, and that there will be a 50% chance they will assigned to **Usual Care**, which means outpatient routine follow-up exclusively at Dana-Farber in Boston.

Once recruited, all study participants will be registered in the DFCI OnCore Clinical Trial Management System by the Research Assistant. Institutions will register eligible participants in the Clinical Trials Management System (CTMS) OnCore as required by DF/HCC SOP REGIST-101. When required by REGIST-101, registration must occur prior to the initiation of protocol-specific procedures or assessments.

Registration requires a signed informed consent document and a completed eligibility checklist according to DF/HCC SOP REGIST-104.

Patient enrollment happens after stem cell infusion. Patients will not be enrolled if the transplant is canceled prior to Day 0.

5.0 STUDY DESIGNS AND METHODS

5.1 DESIGN/ STUDY TYPE

We propose a randomized control trial with two arms. Participants will be randomized 1:1 to the intervention arm (Shared Care) or to the conventional arm (Usual Care). Randomization will be stratified by site and conditioning intensity (Full vs Reduced intensity).

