6.2 PATIENT-REPORTED OUTCOMES (POWERED ON FACT-BMT)

Our primary hypothesis is that patients in the Shared Care group will have improved PROs compared to those in Usual Care due to a decreased burden of traveling and/or relocation to the HCT center. To investigate this hypothesis, the primary endpoint of this aim is powered by an expected improvement in FACT-BMT score between Shared Care to Usual Care 180 days post HCT. Of the total 324 patients who are randomized at study entry, we project that 80% will be alive at six months after allogeneic HCT and 70% will participate in the day 180 PRO assessment. These projections are based on survival data of DFCI HCT patients between 2012 and 2015, and the response rate from our prior survey regarding financial hardship experienced at 180 days after HCT described above (DFCI RR=72%; Table 5). This yields a sample size of 180. In a previous study of QOL for patients after allogeneic HCT, the mean FACT-BMT score at 100 days after HCT was 110 (± 20).¹⁹ Therefore, we believe a difference of 20 or more will be meaningful to show improved PROs at a similar time period (day 180). Extrapolating from this information, if the FACT-BMT score is 120 for Shared Care and 100 for Usual Care at 180 days post-HCT, there will be >99% power to detect this difference. If, however, the difference is 10, then there will be 90% power to detect this difference. This power calculation is based on asymptotic power of the Wilcoxon-Rank-Sum test against an alternative shift at the two sided significance level of 0.05, assuming the standard deviation of the difference is 20. An additional preliminary endpoint is expected difference in mean PSS-4, one of the potential quality of life surveys, score at day 180 post-HCT. In our financial hardship survey, the mean PSS-4 score for DFCI allogeneic patients (n=139) was 5.6 (± 3.2). Extrapolating from these data, if the difference in PSS-4 between the Shared and Usual Care groups is 2 with standard deviation 3.2, there will be 98% power to detect this difference at the two-sided significance level of 0.05.

Table 3. Sample DFCI Allogeneic HCT Patient Characteristics (n=139)

Patient Characteristics	%*
Diagnosis	
Acute Myeloid Leukemia	35
Myelodysplastic Syndromes (MDS)	20
Myeloproliferative Neoplasms	15
Acute Lymphoblastic Leukemia	15
Other	15
Sex	
Female	41
Male	59
Age	
60 or under	50
Over 60	50
Race	
White	96
Non-white	4
Insurance Type	
Employer sponsored	64
Government sponsored	29
Self-insured	7

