approaches to handling missing data from dropouts. First, to assure PRO scores for non-responders are missing at random, we will perform a sensitivity analysis comparing the patient, HCT characteristics, and clinical outcomes between responders and non-responders. Second, we will perform multiple imputation on the outcome variable (including all independent variables) and compare the result without multiple imputation (i.e., inclusion of responding patients only). More importantly, with voluntary patient consent to participate in the study and proactive collection of survey data by the research team, we anticipate that the non-compliance rate will be minimal (<5%). Moreover, we anticipate that there will be no missing independent variables in all HCT patient-related data as this data must be reported to the CIBMTR database by the DFCI/BWH HCT center. Finally, to assure the robustness of our results, we will compare the FACT-BMT scores of the randomized Usual Care cohort with the non-randomized usual care cohort.

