treating relapse as a competing event, with the latter being the primary analysis. In the competing risks data analysis, we will examine whether the competing event of relapse is similar between the two types of care. Other endpoints in this aim include overall survival, progression-free survival, NRM, relapse, and a/c GVHD. For overall and progression-free survival, standard survival analysis will be performed, including the Kaplan-Meier method for estimation of survival functions, log-rank test for comparison of KM curves, and Cox proportional hazards model for multivariable regression analysis. For NRM, relapse and a/c GVHD, competing risks data analysis will be performed. Since these endpoints are immunologically intertwined, it is critical to analyze them in a competing risks framework.^{20,21} In addition, we will perform a sensitivity analysis comparing baseline characteristics and clinical outcomes between the Shared Care and the non-randomized usual care group, and between the randomized Usual Care group and the non-randomized usual care group. Again, we anticipate no missing data in HCT clinical outcomes since reporting of HCT-related outcomes data to the CIBMTR is mandatory

Table 4. Pre-specified Attributes to Examine Heterogeneity

Patient attribute	Age Patient sex CMV seropositive status
Donor attribute	Donor sex Donor type: related vs. unrelated HLA type: matched vs. mismatched CMV seropositive status
Disease attribute	Blood Cancer Diagnosis Disease status
Transplant attribute	Conditioning intensity GVHD prophylaxis Graft source

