6.5 HETEROGENEITY IN TREATMENT (HTE) EFFECTS

Heterogeneity of the group effect (Shared Care vs. Usual Care) on outcomes will be examined for pre-specified patient, donor, disease and transplant related attributes (Table 4). The attributes

Version 8 , 11/16/2020

shown are known risk factors for allogeneic HCT. Since this is a randomized study, we anticipate that all these attributes will be well balanced between two groups. With respect to patient gender and ethnicity, we are aware of no data that would lead us to expect differential effects of treatments in allogeneic HCT by gender and ethnicity. However, when the proposed study is completed, we will perform a multivariable linear regression analysis on FACT-BMT and PSS-4 including attributes shown in Table 4 and type of care (Shared vs. Usual) to identify factors associated with a better outcome. In addition, we will test interactions between each group (Shared vs. Usual) and attributes. If any of these attributes perform better in one group over the other, we will report the results to facilitate further investigation in future studies.

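### Randomisation is stratified by site and conditioning intensity, but the only FACT-BMT test named carries neither factor and site enters no FACT-BMT comparison in the supplied text; adjusting is a small, cheap gain

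*Combined protocol and SAP*

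**What the plan says.** Section 5.1 sets a 1:1 allocation and states: "Randomization will be stratified by site and conditioning intensity (Full vs Reduced intensity". Section 5.52 counts six community sites, so there are 12 site-by-intensity cells.

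Section 6.2 powers the patient-reported aim on day-180 FACT-BMT. On the method it says "This power calculation is based on asymptotic power of the Wilcoxon-Rank-Sum test against an alternative shift", at a two-sided 5% level with SD 20. It names no strata or covariates. For the smaller scenario it says that if "the difference is 10, then there will be 90% power to detect this difference"; for 20 points it claims more than 99%. On numbers, "we project that 80% will be alive at six months after allogeneic HCT and 70% will participate in the day 180 PRO assessment", which it turns into 180 evaluable patients.

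Section 6.5 plans the one FACT-BMT regression: "we will perform a multivariable linear regression analysis on FACT-BMT and PSS-4 including attributes shown in Table 4 and type of care". The transplant row of Table 4 reads "Conditioning intensity GVHD prophylaxis Graft source". No row of Table 4 lists site.

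Section 6.3 adds a sensitivity analysis: "we will perform multiple imputation on the outcome variable (including all independent variables"). Those variables are not listed.

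**The concern.** Stratified allocation balances the arms on the strata. If the strata also predict the score, the arm difference varies less from trial to trial than an unadjusted analysis assumes. The standard error is then too large, the test rejects too seldom under the null, and some power is left unused. Analysing by the factors used to randomise corrects this.

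Here one stratum reaches a regression and the other reaches no FACT-BMT comparison. The trial's rationale makes some site effect plausible, because sites differ in distance from Boston. Section 1.2 reports that long driving time is "associated with a decreased likelihood of being disease-free one year after the procedure", and it links travel costs to financial hardship and hardship to lower quality of life. At stake is a little precision and a clear statement of the primary test, not the validity of the trial.

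**Working it through.** **Inputs from the documents.** 324 randomised 1:1; 80% alive and 70% participating (section 6.2), so 324 x 0.80 x 0.70 = 181, which the plan states as 180; SD 20; two-sided 5%; annual site numbers 21, 20, 20, 14, 14, 20 (section 3.0).

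**Assumptions.** R2 of the two strata together on FACT-BMT of 0 to 15%, half of it through site; permuted blocks of 4 within the 12 cells; a 50/50 intensity split; each patient evaluable at random with probability 0.80 x 0.70 = 0.56. None of these, apart from the 0.56, is in the documents.

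**1. The plan's own power.** Take 90 per arm, a per-patient SD of 20 and the rank-sum efficiency under normality, 3/pi = 0.955. The effective n per arm is 90 x 0.955 = 85.9, and SE = 20 x sqrt(2/85.9) = 3.05. Power for 10 points is Phi(10/3.05 - 1.96) = Phi(1.32) = 90.6%. For 20 points it is Phi(20/3.05 - 1.96), above 99.9%. Both stated figures reproduce.

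**2. Level of an unadjusted test.** Stratification removes the strata's share of the variance of the arm difference among all 324. Random loss to 56% keeps 56% of that reduction. The true variance is therefore (1 - 0.56 R2) times the one the test assumes, and the level is 2[1 - Phi(1.96/sqrt(1 - 0.56 R2))]. For example, at R2 = 15%: 1 - 0.56 x 0.15 = 0.916, 1.96/sqrt(0.916) = 2.05, level 4.1%.

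**3. Simulation** (20,000 replicates per R2, all tests on the same data sets). Entries are percentages.

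| Assumed R2 | 0 | 2 | 5 | 10 | 15 |
|---|---|---|---|---|---|
| Level, unadjusted (closed form) | 5.0 | 4.9 | 4.7 | 4.4 | 4.1 |
| Level, rank-sum | 5.1 | 4.8 | 4.7 | 4.3 | 4.1 |
| Level, adjusted ranks | 5.2 | 5.0 | 4.8 | 4.9 | 4.9 |
| Power for 10 points, normal scores: rank-sum | 90.1 | 90.5 | 90.6 | 90.7 | 91.3 |
| Same, adjusted ranks | 89.6 | 90.6 | 91.2 | 92.3 | 93.8 |
| Power, left-skewed scores: rank-sum | 95.0 | 94.6 | 94.5 | 94.3 | 94.1 |
| Same, adjusted ranks | 94.8 | 94.8 | 95.1 | 95.5 | 96.5 |
| Same, adjusted linear model | 91.3 | 91.3 | 92.2 | 93.5 | 94.8 |

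Adjusted ranks minus rank-sum, before rounding: -0.5 / +0.1 / +0.6 / +1.6 / +2.5 points (normal) and -0.3 / +0.2 / +0.6 / +1.2 / +2.4 (skewed). Monte Carlo error on these paired differences is 0.07 to 0.16 points. Adjusted linear model minus rank-sum under skew: -3.7 / -3.3 / -2.3 / -0.8 / +0.7. The skewed case uses a reflected gamma with shape 4, which is also an assumption.

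**4. Precision of the mean difference** (normal scores). The reported 95% CI half-width is 5.9 points unadjusted, and 5.9 / 5.9 / 5.8 / 5.6 / 5.5 adjusted. Most of that narrowing corrects a conservative SE. The true sampling SD moves from 2.99 / 2.96 / 2.94 / 2.88 / 2.85 to 3.01 / 2.97 / 2.91 / 2.84 / 2.77. It does not fall at R2 of 0 to 2%, and it falls by 0.03 to 0.08 at 5 to 15%.

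**5. Site on its own.** Adding site to a linear model that already has arm and intensity changes power by -0.5 / -0.2 / +0.1 / +0.6 / +0.9 points. At R2 of 5 / 10 / 15% this becomes -0.4 / -0.4 / -0.2 if site carries none of the R2, and +0.6 / +1.7 / +2.9 if it carries all of it.

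**The case against.** The strongest case against is that nothing in the trial turns on this. Section 6.2 treats 20 points as the meaningful difference, and power there is effectively 100% with or without adjustment. That stands: the figures above matter only for the 10-point scenario.

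Evidence for a site effect is thin. Both arms are transplanted and surveyed at DFCI, and section 1.2 speaks of driving time, travel costs and hardship, not of FACT-BMT by site. Patients may choose their centre (section 3.0), so site is an imperfect proxy for distance. Any effect of local care would act only in the Shared Care arm, and an additive site term does not address that. This stands too, and it is why the range of R2 starts at zero.

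The point also rests partly on silence. The rank-sum test is named only for power, so an unadjusted primary analysis is inferred. The unlisted imputation variables could include site, and text just before section 6.1 is missing from the supplied copy. Hence the limit to the supplied text.

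A reader might infer that ignoring the strata inflates type I error or that the power is overstated. The documents support neither: the error runs in the conservative direction and the 90% reproduces. A reader might also infer that both strata are ignored throughout. They are not, since conditioning intensity is in the section 6.5 model, although that model is described as a search for factors associated with outcome and not as the primary comparison.

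What survives is that the analysis does not visibly follow the randomisation, and that aligning it costs almost nothing.

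**Conclusion.** The point holds as a low-severity improvement. In the supplied text, the only FACT-BMT test named is unadjusted, and site is in no FACT-BMT between-arm analysis. If the strata predict the score, the unadjusted test is slightly conservative, with a level between 5.0% and 4.1% for R2 of 0 to 15%. A strata-adjusted rank test would change power for 10 points by about -0.5 to +2.5 percentage points. The size, and at low R2 the sign, rests on an R2 that the documents do not give, and on the assumed blocks, intensity split and random loss.

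**What to change.** Make the primary day-180 FACT-BMT test a strata-adjusted rank test: regress the ranks on arm, site and conditioning intensity, and test the arm term. Report the mean difference with its 95% CI from a linear model with the same three terms, as the supporting estimate. State this order in advance. Making the linear model primary instead could lose about 2 to 4 power points to the rank-sum test if scores are left-skewed and R2 is low.

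First reconcile the site list and state how the stratum is coded. Section 3.0 and the Accrual Monitoring part of the monitoring plan name Lifespan Cancer Institute, where section 5.52 and Table 2 name Stamford Hospital. This is a separate inconsistency, but a site term needs one definition.

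The cost is SAP wording only, since both factors must be recorded in order to randomise. If the strata do not predict FACT-BMT, adjustment loses about 0.3 to 0.6 power points. Adding site to the section 6.5 model is a separate choice: that model already holds 12 Table 4 attributes and plans interactions with about 180 evaluable patients, and the cost of further terms there has not been calculated.
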